### **Endpoint Definitions**

The primary endpoint assessment will be the biochemical response rate defined by normalization of alkaline phosphatase or decrease of alkaline phosphatase by > 40% of the Day 0 level at 24 weeks of treatment.

Secondary endpoints will include:

- Absolute and percent change in alkaline phosphatase from Day 0 to 24 weeks.
- Absolute and percent change in alanine transferase (ALT) from Day 0 to 24 weeks.
- Change in liver stiffness from Day 0 to week 24 as measured by magnetic resonance elastography.
- Change in quality of life measured by change in PBC-40 from Day 0 to week 24.
- Change in AMA titer from Day 0 to week 24
- Change in IgM level from Day 0 to week 24
- Change in CD4+CD44+CD62L- and CD8+CD44+CD62L- frequencies in PBMC from Day 0 to week 24
- Comparisons of safety assessments pre-treatment, on-treatment, and post-treatment including adverse events, laboratory observations, and physical exam findings.
- Trough concentrations of abatacept from week 0 to week 24
- Immunogenicity evaluated over time by measuring serum anti-abatacept antibodies and anti-CTLA-4-T antibodies

### **Analyses**

Endpoints of efficacy will be compared between Day 0 and Week 24 using paired t-test (or Wilcoxon signed rank test as indicated) for continuous variables and Chi-square test

PROTOCOL TITLE: ABATACEPT FOR THE TREATMENT OF PRIMARY  
BILIARY CIRRHOSIS WITH AN INCOMPLETE BIOCHEMICAL RESPONSE TO  
URSODEOXYCHOLIC ACID

(or Fisher's exact test) for categorical variables. For variables measured at multiple time points, Repeated Measures ANOVA will be employed. All analyses will be two-tailed and P values less than 0.05 will be considered as statistically significant.

The primary endpoint assessment will be the biochemical response rate defined by normalization of alkaline phosphatase or decrease of alkaline phosphatase by > 40% of the Day 0 level at 24 weeks of treatment. We will report the observed biochemical response rate and a 95% confidence interval for the expected biochemical response rate.

We will assess each of the secondary endpoints: absolute and percent change in alkaline phosphatase, absolute and percent change in alanine transferase (ALT), change in liver stiffness as measured by magnetic resonance elastography, change in quality of life measured by change in PBC-40, change in AMA titer, change in IgM level, and change in CD4+CD44+CD62L- and CD8+CD44+CD62L- frequencies in PBMC from Day 0 to week 24 by paired t-test or Wilcoxon signed-rank test when appropriate. Because these endpoints will be generated with these studies, to solve the problem of the above multiple significance testing, we will use the false discovery rate proposed by Benjamini and Hochberg. In addition, PK and immunogenicity of abatacept in patients with PBC will be estimated.

Descriptive statistics will be used to summarize safety data to allow a comparison between pre-treatment, on-treatment, and post-treatment. Safety data, including AEs, clinical and laboratory observations and physical examination findings, and other safety related outcomes will be summarized. Summary tables of treatment-emergent AEs will be provided. A treatment emergent AE (TEAE) is any AE that newly appeared, increased in frequency, or worsened in severity following initiation of study medication. AEs will be included in the treatment-emergent analysis if the onset date is on or after the first day of dosing and up to 56 days post the last dosing day. The incidence of TEAEs will be tabulated by system organ class and preferred term for each treatment group, and by severity and relationship to treatment. Tables of TEAEs leading to study medication discontinuation and SAEs will be provided. Descriptive statistics summarizing laboratory data (hematology and chemistry) will be presented for all trial visits. Changes from pretreatment to each trial visit will also be summarized. Additional safety assessments include vital signs, physical examinations, and ECGs.

For safety assessments pre-treatment, on-treatment, and post-treatment including adverse events, laboratory observations, and physical exam findings, repeated measures analysis of variance (ANOVA) will be employed to analyze a continuous outcome variable measured at these multiple time points, and a generalized estimating equation will be used to analyze a count or binary outcome variable measured at these multiple time points in order to take into account a possible unknown correlation among outcomes obtained on the same patient.

**PROTOCOL TITLE: ABATACEPT FOR THE TREATMENT OF PRIMARY BILIARY CIRRHOSIS WITH AN INCOMPLETE BIOCHEMICAL RESPONSE TO URSOODEOXYCHOLIC ACID**

Clinical outcomes will be assessed including death from hepatic and non-hepatic causes, liver transplantation or placement on a liver transplant list, MELD score  $\geq 15$ , new complications of liver disease including DILI as defined above, esophageal variceal bleeding, interventions to manage variceal bleeding, ascites, hepatic encephalopathy, renal failure, spontaneous bacterial peritonitis, and hepatocellular carcinoma.

Summary statistics for abatacept concentrations from Week 0 to Week 24 will be tabulated. Lack of immunogenicity is defined as the absence of a positive antibody response generated against abatacept administered subcutaneously. The incidence of a positive response will be summarized. The data will be analyzed to assess immunogenicity and its potential effect on pharmacokinetics and safety.

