## 12) Procedures Involved

This is an open label, active treatment trial to assess the efficacy and safety of abatacept in subject with PBC who have had an incomplete biochemical response to UDCA.

In this trial, 20 subjects with PBC who have had an incomplete biochemical response to UDCA will be assigned to treatment with weekly subcutaneous injections of 125 mg of abatacept.

The treatment phase of the study will last 24 weeks with an off-treatment follow up at Week 36.

All subjects will undergo blood chemistry panel, complete blood count, INR, AMA, magnetic resonance elastography (MRE), and PBC-40 survey prior to the first dose of study drug. Baseline Mayo Risk Score and MELD score will be calculated from baseline lab values. Subjects will complete the 24 week treatment course and undergo repeat MRE and laboratory testing. Laboratory testing and assessments for adverse events will be conducted at Weeks 2, 4, 12, 24, and 36. Details are given in the Time and Events Schedule.

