**Populations for Analyses**

The primary analysis set for efficacy and safety analyses will include all subjects who received at least one dose of study drug.

**PROTOCOL TITLE: ABATACEPT FOR THE TREATMENT OF PRIMARY BILIARY CIRRHOSIS WITH AN INCOMPLETE BIOCHEMICAL RESPONSE TO URSODEOXYCHOLIC ACID**

**Pharmacokinetic Analysis Population:** All available plasma concentration data from subjects who receive at least 1 dose of study medication and have at least 1 concentration result will be reported. However, only subjects without dose interruption will be included in the summary statistics.

**Immunogenicity Analysis Population:** For immunogenicity samples, included all subjects who receive at least 1 dose of abatacept and have at least 1 immunogenicity result reported.

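### Repeated measures ANOVA for continuous multi-visit variables has no sphericity correction or missed-visit rule; this affects the continuous safety comparison and supportive analyses, not the primary result

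*Combined protocol and SAP*

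**What the plan says.** Under Statistical Considerations, the Analyses section gives a general rule: "For variables measured at multiple time points, Repeated Measures ANOVA will be employed". The safety paragraph of that section adds that "repeated measures analysis of variance (ANOVA) will be employed to analyze a continuous outcome variable measured at these multiple time points", with generalized estimating equations for counts and binary outcomes.

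Four other statements bear on this:

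- Populations for Analyses: "The primary analysis set for efficacy and safety analyses will include all subjects who received at least one dose of study drug".
- Endpoint Definitions lists as a secondary endpoint: "Comparisons of safety assessments pre-treatment, on-treatment, and post-treatment including adverse events, laboratory observations, and physical exam findings".
- Section 12, Procedures Involved: "Laboratory testing and assessments for adverse events will be conducted at Weeks 2, 4, 12, 24, and 36".
- Analyses, for the named continuous efficacy endpoints (alkaline phosphatase, ALT, liver stiffness, PBC-40, AMA, IgM and the T-cell frequencies): change is tested "from Day 0 to week 24 by paired t-test or Wilcoxon signed-rank test when appropriate", and for multiplicity "we will use the false discovery rate proposed by Benjamini and Hochberg".

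The safety paragraph also promises summaries that do not depend on the ANOVA: "Descriptive statistics summarizing laboratory data (hematology and chemistry) will be presented for all trial visits", together with changes from pretreatment at each visit.

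**The concern.** Classical repeated measures ANOVA has two properties that fit this trial poorly.

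1. **Complete profiles only.** A subject who misses one visit that serves as a level leaves the analysis, although the plan's set is everyone dosed at least once.
2. **Sphericity.** The F test is exact only if all pairwise differences between visits have the same variance. With gaps of 2 to 12 weeks between visits, that is doubtful.

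At stake is the pre-, on- and post-treatment safety comparison. For its continuous variables this ANOVA is the only inferential test named, and the plan applies a two-tailed 0.05 threshold to all analyses. Also exposed are variables scheduled at several visits but absent from the paired-test list, such as CRP, lipids, IgG and IgA. For alkaline phosphatase, ALT, AMA, IgM and the T-cell frequencies, both the general ANOVA sentence and the paired tests apply, and the plan does not say which governs.

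**Working it through.** **Inputs from the documents.** Up to 20 subjects; two-sided 0.05; laboratory visits at Weeks 2, 4, 12, 24 and 36 plus baseline.

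**Assumptions, because the documents give no figures.** Five to 10% of post-baseline visits are missed, independently and at random, with baseline present. Correlation between visits decays with time: 0.7 to 0.95 per 6 weeks, with 0 to 20% of the variance being measurement noise.

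**The plan's own figures.** None is given for the ANOVA. The Sample Size Determination figures reproduce with the exact binomial: P(X ≤ 3 | 20, 0.05) = 98.4% (stated as above 98%) and P(X ≥ 4 | 20, 0.30) = 89.3% (stated as 89%). Neither involves the ANOVA.

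**Step 1: subjects kept.** Expected number = 20 × (1 − m)^v, where m is the missed-visit rate and v is the number of post-baseline visits needed.

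| Visits needed | m = 5% | m = 10% |
|---|---|---|
| Weeks 2, 4, 12, 24, 36 (v=5) | 20 × 0.95^5 = 15.5 | 20 × 0.90^5 = 11.8 |
| Four visits (CRP, or laboratory tests through Week 24) | 16.3 | 13.1 |
| Weeks 12, 24, 36 (lipids, v=3) | 17.1 | 14.6 |
| Weeks 24 and 36 only (v=2) | 18.1 | 16.2 |

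**Step 2: type I error of the F test.** Departure from sphericity is measured by ε = (tr A)² / [(k − 1) tr(A²)]. Here A is the doubly centred covariance matrix of the k visits, and ε = 1 means sphericity holds. Rejection rates of a true null come from 20,000 simulated trials per setting, n = 20, no missing data (Monte Carlo error about 0.2 points).

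| Levels | ε | Uncorrected | Greenhouse-Geisser |
|---|---|---|---|
| Weeks 0, 2, 4, 12, 24 | 0.47 to 0.92 | 5.2 to 9.4% | 3.7 to 5.1% |
| The same plus Week 36 | 0.40 to 0.85 | 6.1 to 10.2% | 4.0 to 4.9% |
| Weeks 0, 24, 36 | 0.78 to 0.95 | about 5 to 6% | about 4 to 5% |

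If correlation does not decay, the uncorrected test is at about 5%.

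**Step 3: precision.** The simulated SD of the Week 24 change was compared between complete-visit analysis and a mixed model (assumed SD 0.30, correlation 0.9 per 6 weeks, 10% noise; Monte Carlo error about 2%).

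- Visits through Week 24: 0.0659/0.0598 = 1.10 at 5% missed; 0.0743/0.0611 = 1.22 at 10%.
- Visits through Week 36: 0.0695/0.0613 = 1.13 and 0.0803/0.0618 = 1.30.
- Planned paired test against the mixed model, same four settings: 0.0604/0.0598 = 1.01 to 0.0640/0.0618 = 1.04.
- Drop-out before Week 24 only, 10% or 20% in total: 0.0656/0.0649 = 1.01 and 0.0677/0.0656 = 1.03. Complete-visit and paired analyses then keep the same 18 or 16 subjects.

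**Step 4: does the replacement behave at n = 20?** A spatial-power mixed model with Kenward-Roger degrees of freedom alone gave 13.9 to 14.6% type I error for the Week 24 contrast when subjects differed in slope (assumed slope SD 0.30 over 24 weeks). A bias-reduced robust standard error with t on n − 1 degrees of freedom gave 3.3 to 5.0% in every setting tried, with 0, 5 or 10% of visits missed. With no missed visit it reproduces the paired t-test exactly.

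**The case against.** The strongest counter-argument is that the safety sentence refers to pre-, on- and post-treatment assessments, so its time points may be three phases rather than six visits. That reading is reasonable, and under it the problem shrinks. About 18 to 16 subjects are kept if Weeks 24 and 36 are needed, and 19 to 18 if any on-treatment visit will do. Type I error is about 5 to 6% for Weeks 0, 24 and 36, or about 6 to 8% if the on-treatment visits are averaged. Footnote 1 of the Time and Events Schedule also asks for the Week 36 assessments at discontinuation, and section 16 expects follow-up after stopping. The plan does not say which levels apply, so the ambiguity is itself part of the point.

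Some software fits repeated measures ANOVA as a mixed model or applies a correction. The claim therefore holds only for the standard form. The plan names no implementation, which leaves that choice open until data are seen.

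The paired tests also omit subjects without Week 24 data. They lose far fewer, however, because they need only two time points.

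A reader might infer that the trial's efficacy conclusion is compromised. The documents do not support this: the response rate is reported with a 95% confidence interval, and the named efficacy changes use paired tests. A reader might also take the 10 to 30% loss of precision as a general cost. It rests on assumed intermittent missed visits and all but disappears if missing data are drop-out only. Nor does safety oversight hang on these p-values: the plan provides descriptive summaries at every visit and Data Monitoring Committee review.

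**Conclusion.** The point holds in a limited form. The plan names a method that, in its standard form, can drop dosed subjects and reject too often, and it is the only inferential test named for continuous safety changes within a listed secondary endpoint. Type I error is about 5 to 10% with every scheduled visit as a level and about 5 to 6% with Weeks 0, 24 and 36 only, provided correlation decays and no correction is applied. Subjects kept range from about 15.5 to 11.8 down the full visit list to about 18 to 16 for Weeks 24 and 36, at an assumed 5 to 10% missed per visit. If no visit is missed and a correction is already applied, nothing is gained by changing. The primary response rate, the go/no-go rule in Sample Size Determination and the paired endpoint tests are untouched. The change is advisable rather than essential. Statements that the plan is silent refer to the supplied text, from which some pages were removed.

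**What to change.** In both places in the Analyses section:

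1. State which time points are the levels for each variable, including how the Pre-Treatment and Day 1 values form the baseline.
2. Replace repeated measures ANOVA with a likelihood-based mixed model on all available data, with visit as a categorical factor and a working covariance named in advance that allows unequal spacing (for example spatial power plus residual error). Report Week 24 minus Day 0 and Week 36 minus Day 0 as separate contrasts.
3. Prespecify one inference method: the bias-reduced robust standard error with t on n − 1 degrees of freedom, always used. A rule for switching between standard errors would invite a data-dependent choice.
4. Keep the paired t or Wilcoxon tests as the endpoint tests entering Benjamini-Hochberg, and label the mixed model supportive for those endpoints.

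If ANOVA is kept, at minimum apply Greenhouse-Geisser and report the number of subjects analysed. That corrects the type I error but does not recover subjects with missed visits.

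**Cost.** SAP wording and slightly more programming; no new data, visits or subjects. The model brings a working covariance assumption with only 20 subjects, and it is valid only if missingness depends on observed values. The robust standard error protects the test against a wrong covariance, but it does not remove bias in the estimate when missingness depends on earlier values and the covariance is badly wrong.

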**Figure 1. Study Design Schematic**

Screening	Abatacept 125 mg SC				Off-Treatment FU	
Week	0	2	4	12	24	36

PROTOCOL TITLE: ABATACEPT FOR THE TREATMENT OF PRIMARY BILIARY CIRRHOSIS WITH AN INCOMPLETE BIOCHEMICAL RESPONSE TO URSODEOXYCHOLIC ACID

Time and Events Schedule for Protocol [IM101-457]

Procedures	Pre-Treatment Visit	Treatment Day 1	Treatment Week 2	Treatment Week 4	Treatment Week 12	Treatment Week 24	Post-Treatment Week 36 
Eligibility Assessments							
Informed Consent	X						
Inclusion/Exclusion	X						
Medical History							
Safety Assessments							
Physical Exam	X					X	
Vital signs	X	X	X	X	X	X	X
Signs and Symptoms		X	X	X	X	X	X
Adverse Events		X	X	X	X	X	X
ECG	X						
PPD	X						
HCV antibody	X						
HBs antigen	X						
HIV antibody	X						
UPT 	X	X		X	X	X	
Efficacy Assessments							
CMP	X	X	X	X	X	X	X
CBC	X	X	X	X	X	X	X
INR	X	X	X	X	X	X	X
CRP	X			X	X	X	X
AMA	X	X	X	X	X	X	X
IgG, IgM, IgA	X	X	X	X	X	X	X
ANA	X	X	X	X	X	X	X
Lipid Panel	X				X	X	X
MR Elastography	X					X	
PBC-40	X					X	
CD44+CD62L-	X				X	X	X
PK/IMG Samples 		X		X	X	X	X
Clinical Drug Supplies							
Abatacept 125 mg SC once weekly		X	X	X	X	X	

 Also to be performed for any subjects discontinuing the study with documentation for reason for discontinuation.

 Weeks 4, 12, and 24 should be drawn pre-dosing. The precise PK sampling times relative to the actual dosing time must be accurately recorded on the eCRF. The date and time of sample collection must be recorded so that compliance with the sampling schedule can be confirmed.

PROTOCOL TITLE: ABATACEPT FOR THE TREATMENT OF PRIMARY  
BILIARY CIRRHOsis WITH AN INCOMPLETE BIOCHEMICAL RESPONSE TO  
URSODEOXYCHOLIC ACID

From the ICF:

The clinical study will be done only at UC Davis. The name and address of this study center and the investigator for this study center are listed on page 1 of this document. Authorized members of the study staff will do all study procedures.

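### The test of adverse events across treatment periods has no time-at-risk term, although treatment lasts 24 weeks and post-treatment follow-up 12

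*Combined protocol and SAP*

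**What the plan says.** The secondary endpoints (section 11, and Endpoint Definitions in section 14) include a comparison of safety across the pre-, on- and post-treatment periods. The Analyses text first describes this comparison descriptively, then adds a model: "For safety assessments pre-treatment, on-treatment, and post-treatment including adverse events, laboratory observations, and physical exam findings", repeated measures ANOVA is used for continuous outcomes and "a generalized estimating equation will be used to analyze a count or binary outcome variable measured at these multiple time points". The stated reason for the GEE is correlation within a patient. Duration of observation is not mentioned. The same section makes every analysis two-tailed at P<0.05.

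Section 10 sets a 24-week treatment phase with an off-treatment follow-up at Week 36. Section 12 states: "Laboratory testing and assessments for adverse events will be conducted at Weeks 2, 4, 12, 24, and 36". In the Time and Events Schedule:
- the row "Abatacept 125 mg SC once weekly" is marked from Day 1 to Week 24;
- the row "Adverse Events" is blank at the Pre-Treatment Visit and marked from Day 1 to Week 36;
- the row "Physical Exam" is marked at the Pre-Treatment Visit and Week 24 only.

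For the separate treatment-emergent tables, an AE qualifies if its onset is "on or after the first day of dosing and up to 56 days post the last dosing day".

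**The concern.** The periods being compared differ in length by a factor of two, and the visit intervals within treatment are unequal. A model of incident AEs without time at risk compares amounts of observation as well as AE rates. The direction of the error depends on data layout. Period totals favour an apparent fall after stopping, which reads as drug toxicity. Visit-interval counts favour an apparent rise, which reads as withdrawal harm or as protection while on drug.

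Safety is the first secondary objective and the trial has no control arm, so this is the plan's stated inferential comparison of AEs over time.

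**Working it through.** The plan gives no operating figure for this test, so there is none to reproduce.

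**Inputs from the documents.** 20 subjects (section 7); 24 weeks on treatment and 36 − 24 = 12 weeks after (section 10); AE visits at Weeks 2, 4, 12, 24 and 36 (section 12), giving intervals of 2, 2, 8, 12 and 12 weeks; two-sided 0.05 (section 14).

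**Expected ratio with no drug effect.** Let λ be a constant AE rate per subject-week.
- One record per period: on/post = 24λ / 12λ = 2.0.
- One record per visit interval: mean on-treatment interval = (2 + 2 + 8 + 12)/4 = 6 weeks, so on/post = 6λ / 12λ = 0.5.
- Offset log(weeks): each count is divided by its own weeks at risk, so on/post = λ/λ = 1 in either layout.

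**Size of the error.** No document gives an AE rate. Assume 24-week probabilities p of at least one AE of 30%, 50%, 70% and 90%, with λ = −ln(1 − p)/24, Poisson counts, no dropout and no drug effect. Each cell rests on 1000 simulated trials of 20 subjects. In the count analyses, trials with an empty period count as no rejection.

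| Assumed p | 30% | 50% | 70% | 90% |
|---|---|---|---|---|
| Expected AEs per subject in 24 weeks, −ln(1 − p) | 0.36 | 0.69 | 1.20 | 2.30 |
| Pooled counts, no offset: false fall | 15% | 33% | 55% | 81% |
| Pooled any-AE (binary), no offset: false fall | 12% | 29% | 37% | 22% |
| Visit-interval counts, no offset: false rise | 25% | 36% | 53% | 75% |
| Pooled counts with offset: all false positives | 4% | 6% | 7% | 6% |
| Visit-interval counts with offset: all false positives | 4% | 5% | 7% | 8% |
| Week 24 vs Week 36 interval only, no offset: all false positives | 3% | 5% | 7% | 6% |

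A repeat simulation gave similar ranges: 14–80% (pooled counts), 11–33% (binary) and 24–72% (visit intervals).

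**Sensitivity to the model.** A second simulation let AE rates vary between patients (gamma frailty, variance 0.5), used an exchangeable working correlation and assumed 1, 2, 4 and 8 AEs per patient-year (400 trials each). Without the offset, false falls on pooled counts were 25%, 43%, 73% and 93%, and false rises on visit intervals were 29%, 44%, 67% and 90%. The any-AE version gave 17–28% and 28–68% respectively. With the offset, all false positives were 4.5–8.0%. A small excess over 5% is consistent with robust standard errors on 20 clusters.

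**Where the offset would be wrong.** Suppose the outcome is whether an AE is present on the visit day, with constant prevalence q. Interval length is then irrelevant, and the unadjusted test is sound: 4–5% false positives at q = 10%, 20%, 30% and 50%. An offset would compare 4q/24 = q/6 with q/12, a spurious post/on ratio of 0.5, and falsely show a fall in 1%, 19%, 46% and 85% of trials.

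**The case against.** **Silence is not exclusion.** The plan names a class of model and also omits link, working correlation and covariates; a competent analyst might well add an offset. That is fair, and a reader should not infer that the trial will be analysed without one. But the plan describes a test at P<0.05 and gives nothing that protects it from unequal observation time.

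**Some readings are unbiased.** A visit-day prevalence outcome, or a direct contrast of the two 12-week intervals ending at Weeks 24 and 36, escapes the problem. This stands, and it means an offset is not right for every counting unit. Neither analysis is specified.

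**The size is assumed.** This also stands: the AE rates are hypothetical, and the binary version shows a smaller error on pooled data than the count version does.

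**Unseen text.** The reviewed text has gaps. The Analyses section cites a definition of DILI given above that does not appear in it, so a counting rule could lie elsewhere. The finding is limited to the visible text.

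**Little consequence.** The descriptive tables carry most of the safety reporting, and a repaired test remains weak. If a doubled AE rate lasted 56 days past the last dose, an assumption no document supports, power would be only 5–17% over the same AE probabilities (now the off-drug values). This limits the weight of the point, but does not justify keeping a test that can mislead in either direction.

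**Two stronger readings are not supported.** First, a reader might infer that the 56-day window (to Week 24 + 8 = 32, if the last dose is at Week 24) contradicts the post-treatment period. It governs inclusion in the treatment-emergent tables, and nothing says the period test uses it. Second, a reader might infer that no AEs are recorded before dosing. The schedule's Medical History row is blank in every column, so a blank cell is weak evidence, and the treatment-emergent definition ("newly appeared, increased in frequency, or worsened in severity following initiation of study medication") implies some earlier record.

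**Conclusion.** The concern holds for an analysis of incident AEs. The 2.0 and 0.5 expected ratios follow from the protocol's own schedule. The false-positive rates (about 15–81% for pooled counts, about 11–37% for the pooled any-AE version, about 25–75% for visit-interval counts, and about 4–8% with the offset) rest on a constant AE rate, no dropout and assumed AE probabilities.

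Two lesser points belong with it. In the visible schedule, the pre-treatment AE level has no scheduled assessment and the physical exam has no post-treatment value, so those contrasts may lack data.

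The effect is confined to a secondary safety test. The primary endpoint, the go criterion, the treatment-emergent tables and DMC review do not depend on it.

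**What to change.** In section 14 (Analyses), with matching words in the secondary endpoint lists:
- Analyse on- versus post-treatment incident AEs, assigned by onset date with post-treatment starting after the last dose, as counts by Poisson GEE with offset log(subject-weeks at risk). Report rates per subject-week and the rate ratio with a 95% confidence interval.
- State that the offset is not used if the outcome is AE presence on the visit day.
- Include a pre-treatment level in the AE test only if AEs are recorded from consent, and then with the same offset.
- Compare physical exam findings between the Pre-Treatment Visit and Week 24 only.
- Optionally, add a sensitivity analysis that counts the first 56 days after the last dose as on-treatment. It leaves 12 − 8 = 4 off-drug weeks and will be imprecise.

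The cost is a few lines of text and one model term, with no added visit or procedure. Onset dates are already needed for the treatment-emergent window, and time at risk follows from dosing and visit dates. Two limits remain. Power is low with 20 subjects, and an offset cannot correct unequal ascertainment (four scheduled assessments from Week 2 to Week 24, one afterwards). The rate ratio should therefore be read as descriptive support.
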